The resulting effect of this integrated synergy will be to promote greater functional gains (primary hypothesis) at the end of 12 weeks of home- based exercise training and to promote better maintenance of the benefits of pulmonary rehab at 24 weeks than in the no-music group (secondary hypothesis).

C.1.2. General Overview of Design. The proposed study has been designed as a randomized, controlled clinical trial in which COPD patients will be randomized into an exercise program with RAS-enhanced music (RAS- music group) or in an exercise program without music (no-music group). COVID 19 patients will be randomized into an exercise program with RAST-enhanced music (RAST- music group and strength training) or in an exercise program without music (no-music but will have strength training group). Patients will complete testing procedures at pre-randomization, at 6 weeks, immediately post-rehabilitation, and 24 weeks after enrollment. Testing at 6 weeks is included to provide interim follow-up should patients not complete the 12 weeks of training.

C.1.3. Sample Size Calculation.

Sample size was estimated based on a 2-group mixed model design with baseline, 6 and 12-week measurements. Our primary goal is to compare the difference in distance walked during the standard 6MWT over 12 weeks between groups (see **C.1.9.1.a.**). We estimate that the COPD target sample size of 68 patients per group completing 12 weeks will ensure 80% power to detect the differences between treatment arms using a two-sided significance level of 0.05, assuming a correlation of 0.70 between measurements. These estimates are based on our PAD pilot data and include similar standard deviations at baseline and at 6 weeks between groups and over time (232 feet), correlations between measurement of 0.76 to 0.86, and an increase of 87.2 feet at 6 weeks for the RAS- music group, with a slightly higher level for those completing the 12-week assessment. Based on the work of

Table. 2 COPD Study inclusion and exclusion criteria

Inclusion Criteria	Exclusion Criteria
• ≥ 40 yr. of age	• Respiratory infection/COPD exacerbation within the previous four weeks
• FEV ₁ ≤ 70%	• Exercise-limiting heart disease (Congestive heart failure – i.e., New York Heart Association Class III or IV; positive stress test or other indicators of heart disease or complaints of angina during the stress test)
• FEV ₁ /FVC <70%	• Exercise-limiting peripheral arterial disease (stops walking due to intermittent claudication)

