patients. The exercise physiologists, will assist with follow-up exercise, and will ask patients standardized questions regarding dyspnea, angina and ability to continue exercising.⁹⁸ She will be blinded to group assignment. The project manager ([name]) and exercise physiologist ([name]) and the statistician ([name]) will be aware of patient's group assignment.

Exercise Prescription. Upon randomization, all patients will receive a 1-hour educational session on exercise rehabilitation.

Specifically, the clinical exercise physiologist will work with patients to: (1) set up a schedule that fits with

Table. 4 Testing schedule

	Measure(s)	Screen/ Baseline	6- wks	12- wks	24- wks
Eligibility/Screening					
• FEV ₁ ≤ 70% FEV ₁ /FVC <70%	Pulmonary function test	x			
• Eligibility	History, Mini-Mental test	x			
• Co-morbidities	Charlson Index	x			
• Demographics	Demographic data information	x			
• Usual/leisurely walking cadence	Leisurely-paced 6MWT	x			
Primary Dependent Variable					
• Walking distance	Standard 6MWT	x x	x	x	x
Secondary Dependent Variables and Independent Variables					
• Dyspnea onset • Exercise duration (Treadmill walking time)	Constant-load treadmill test	x x	x	x x	x x
• QoL, Dyspnea, Self- efficacy, Physical Function	Questionnaires (SF-36, CRQ, Self-efficacy for walking) COVID 19 CAS	x	x	x	x
• Adherence	Fitbit Step Counts	x	x	x	x
• Daily physical activity	Step counts	x	x	x	x

Definition of abbreviations: 6MWT = six minutes walk test; QoL = quality of life

the patients' schedule for home-based exercise by with his/her usual daily schedule; (2) identify time-slots for exercise; (3) provide information on exercise tips; (4) address perceived barriers to exercise, (5) provide contact information, and (6) build a relationship with patients to provide support and identify health concerns.

C.1.6.1 Exercise Prescription:RAS/RAST-music group

C.1.6.1.a. Music selection: *Immediately after randomization, COPD patients in the RAS-music group will be asked to list 15 songs/music pieces within the one or more genres they most enjoy. If patients need help naming songs/music pieces, we will present them with a catalogue of "Top Twenty" songs/music within several genres. Patients will be also informed that they can choose songs/music not listed in the catalogue.*

COVID 19 patients in the RAST music group will meet with a music therapist at baseline and other timelines to complete their music assessment and music choices.

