H1A: IN PATIENTS WITH COPD, IMPROVEMENTS IN 6-MINUTE WALKING DISTANCE WILL BE GREATER AFTER COMPLETING 12 WEEKS OF A HOME-BASED, EXERCISE PROGRAM WITH RAS-ENHANCED MUSIC THAN AFTER A HOME-BASED, EXERCISE PROGRAM WITHOUT MUSIC.

The analysis of the primary outcome (improvements in 6-minute walking distance) is based on all data collected during the intervention period—baseline, 6 and 12-weeks. We will use a mixed-model analysis that includes treatment, time and treatment-by-time interaction terms. Specifically, we will test whether the treatment- by-time interaction differs from 0. This model will automatically account for missing data

where missing at random is assumed. We will conduct a sensitivity analysis^{129,130} based on the results of the mixed model analysis to determine whether other assumptions regarding the missing data may produce different results. One component of the sensitivity analysis will also include adjustment for

baseline demographic and health covariates.

C.2.2. Statistical Analysis: Secondary Hypotheses

Statistical analysis for H_{1c} will parallel that of H_{1a} .

H_{1D} : THE RAS-ENHANCED MUSIC GROUP WILL DEMONSTRATE GREATER INCREASES IN HEALTH-RELATED QUALITY OF LIFE (QOL) THAN THE CONTROL GROUP.

Statistical analysis for H_{1d} will parallel that of H_{1a} .

H_2 : THE RAS-ENHANCED MUSIC GROUP WILL ACCUMULATE A GREATER VOLUME OF DAILY PHYSICAL ACTIVITY THAN THE CONTROL GROUP. THIS WILL BE DEMONSTRATED BY GREATER PHYSICAL ACTIVITY AT 12 WEEKS (ACTIGRAPHY).

Statistical analysis for H_2 will parallel that of H_{1a} .

H_3 : THE RAS-ENHANCED MUSIC GROUP WILL MAINTAIN IMPROVEMENTS IN MEASURED AND PERCEIVED FUNCTION AT 24 WEEKS TO A GREATER EXTENT THAN THE NO-MUSIC CONTROL GROUP.

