In the statistical analysis of H_3 , we will use independent t-tests to compare the changes in measured function (distance walked in the 6MWT and perceived function (questionnaires) between 12 and 24-weeks between the RAS-music and the no-music groups. We will also conduct paired t-tests within each group to determine whether values at 24 weeks are worse than those at 12 weeks. These computations will be based on those patients with 12 and 24-week data. To assess whether patients included in the H_3 analysis are representative of the original randomized groups, we will also compare demographic and health measures (i.e., FEV₁ percent predicted, comorbidities, depressive symptoms and exacerbations) of patients included in the H_3 analysis to patients who were not.

C.2.3. Statistical Analysis: Exploratory objective: [exploratory objective not reported]

TO ASSESS IMPACT OF PHYSIOLOGICAL AND PSYCHOLOGICAL PHENOTYPE AND CLINICAL FACTORS ON RESPONSIVENESS TO REHABILITATION ACHIEVED WITH AND WITHOUT CONCURRENT USE OF RAS-MUSIC. PHYSIOLOGICAL FACTORS INCLUDE: SYSTEMIC INFLAMMATION (HS-CRP), QUADRICEPS STRENGTH, RECRUITMENT AND FATIGUE, QUADRICEPS FUNCTION AND DIMENSION AFTER REHABILITATION. PSYCHOLOGICAL FACTORS INCLUDE: SELF-EFFICACY, ANXIETY AND DEPRESSION. CLINICAL FACTORS INCLUDE: ADHERENCE TO THE 12-WEEK PROGRAM, ADHERENCE TO FOLLOW-UP AND NUMBER AND SEVERITY OF EXACERBATIONS.

To assess the impact of the above confounders two separate analyses will be conducted: (a) A linear regression model with changes from baseline to 12 weeks of training as the dependent variable, and assigned treatment group, physiologic and psychologic phenotype and clinical factors as the independent variables, and

(b) A mixed model ANOVA with baseline, and 12 and 24 weeks measurements as dependent measures and assigned group, physiologic and psychologic phenotype and clinical factors as the independent variables.

C.3. Expected Outcome: We expect to demonstrate that improvements in 6-minute walking distance from baseline to 12 weeks will be greater after completing 12 weeks of a home-based, exercise program with RAS- music than after a home-based, exercise program without music.

C.4. Alternative Outcomes. Our primary hypothesis will be rejected if, at 12 weeks, improvements in 6-minute walking distance are not greater with exercise-training plus RAS-music than with exercise-training without music. In this case, at least three alternative outcomes will be considered.

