Three, limited adherence to home-based exercise: please see point One, *section C.4.2.*

C.4.4. Miscellaneous limitations and alternative methods

C.4.4.1. Medications: Medications may be adjusted throughout the study; such adjustments may affect outcome variables including exercise endurance. *Proposed Action:* Patients must be on stable therapy before enrollment. From our previous experience, we expect that several patients will require minor adjustments of their anti-hypertensive medication throughout the study. Medication lists and doses will be documented at each evaluation period. If patients require significant medication changes as judged by Drs. [name] (Pulmonary) or [name] (Data Safety Monitoring), appropriate statistical adjustments will be made.

C.4.4.2. Patients withdrawal: Patients may withdraw from the study at a higher rate than anticipated. *Proposed Action:* Since we use intent-to-treat analysis, any patient completing at least six weeks of training will be included in the analysis. If more than 20% of patients withdraw - or have to be withdrawn - prior to the sixth week of training, we will increase the number of randomized patients accordingly.

C.4.4.3. Lack of internet access: Some patients have no internet access. (Patients need internet access to sync the Fitbit). *Proposed Action:* Patients without internet access will be provided with a list neighborhood locations with Wi-Fi hotspots. Alternatively, patients will be free to come to the lab to sync

the Fitbit.

C.4.4.4. Music in the control group: Some patients in the control group may be used to listening to music while walking. *Proposed Action: Through the study, patients in the no-music group will be instructed to avoid listening to any music while walking.* In addition, at the end of the study, we will ask patients in the control group whether they listened to music while walking. Appropriate statistical adjustments will be made if needed.

C.5. Potential Problems.

C5.1. Insufficient patient enrollment. This is a very unlikely considering the large number of patients with COPD cared for at Hines VAH and our excellent track record.^{3,4,80,94} In addition, we could enroll patients from the Jesse Brown VA located 10 miles east of Hines. We could advertise in local newspapers and on Chicago Transit Authority busses.⁹⁶

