C5.2. Exacerbations. Exacerbations can cause functional impairment and decreased peripheral muscle function (see sections **A.3.4** and **C.2.3. Exploratory Objective**). Exacerbations will be tracked as part of our data safety monitoring.

C.5.3. Adherence to the home-based program. In our studies, patient compliance to training has ranged from 90 to 95%.^{3,4,94} In this proposal we will take several steps to ensure high compliance with training (see **C.1.7.**).¹³⁹ All patients will receive at weekly phone calls. In addition, they will be called if they do not sync their Fitbit or do not exercise for three consecutive sessions. Additionally, patients will receive \$20 to cover travel expenses for each visit to the lab.

C.6. Future Directions. If, as we hypothesize, RAS-music plus exercise-training improves exercise capacity at the conclusion of a 12-week home-based rehab program and, thereafter, it promotes the maintenance of physical activity, three questions for future studies will arise: (1) What is the effect of RAS-music plus exercise on the systemic manifestations of COPD including depression, osteoporosis, and coronary artery disease? (2) Could RAS-music plus exercise decrease the staggering health care cost for veterans and non-veterans with COPD?

(3) What is the effect of RAS-music plus exercise on survival? To address these questions, we will pursue a multi-center randomized clinical trial. In addition, we will consider additional studies tailored to specific subgroups of patients. For example, if we find that to achieve and maintain benefits from home-based, RAS-music rehab patients must also develop quadriceps fatigue,^{44,45} we will design an investigation where in “*non-fatigues*” we will combine RAS-music plus a one-leg exercise-training^{41,128} or RAS-music plus neuromuscular electrical stimulation of the quadriceps, gastrocnemius and tibialis anterior muscles.¹²⁶

Risk to Subjects

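### C.4.4.2 names intent-to-treat but ties inclusion to six weeks of completed training, which does not follow from intent-to-treat and is inconsistent with C.2.1

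*Combined protocol and SAP*

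**What the plan says.** Three places in the combined protocol and SAP bear on who enters the primary analysis.

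- **C.4.4.2 (Patients withdrawal)**, the only place in the supplied text that names intent-to-treat: "Since we use intent-to-treat analysis, any patient completing at least six weeks of training will be included in the analysis". It says nothing about patients with less than six weeks of training. The next sentence sets a top-up rule: "If more than 20% of patients withdraw - or have to be withdrawn - prior to the sixth week of training", more patients will be randomised.
- **C.2.1 (primary hypotheses):** the analysis of 6-minute walk distance "is based on all data collected during the intervention period", that is, baseline, 6 and 12 weeks. It is a mixed model assuming data missing at random, with sensitivity analyses, and it sets no training condition.
- **C.1.2 (General Overview of Design):** "Testing at 6 weeks is included to provide interim follow-up should patients not complete the 12 weeks of training".

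One other analysis set is restricted, the one for H3 in C.2.2: "These computations will be based on those patients with 12 and 24-week data". That restriction rests on available data, not on training. No section defines the primary set as all randomised patients.

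**The concern.** Intent-to-treat bases inclusion on randomisation. C.4.4.2 presents a training threshold as its consequence, and training completed is an outcome that the assigned arm can affect. If early stopping, or the result among early stoppers, differs between arms, selecting on completion can create a difference or hide one.

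The patients at issue are those who stop training before week 6 and still attend the 6- or 12-week test. Training is done at home and testing in the laboratory, so stopping one need not end the other. C.2.1 would use these patients' walk distances. C.4.4.2, applied as a rule, would discard them. The missing-data sensitivity analyses in C.2.1 would not repair this, because observed data left out by a set definition are not missing data.

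**Working it through.** **1. The plan's own figure.** Inputs from C.1.3 (COPD): SD 232 ft, correlation 0.70, gain 87.2 ft with music and none without, 68 per group, two-sided 0.05.

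- SD of change = 232 × √(2 × (1 − 0.70)) = 179.7 ft.
- Power at 68 per group = 80.8% (normal approximation), against 80% stated.
- 136 / (1 − 0.20) = 170 randomised, or 85 per arm.

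The sample size reproduces and is not in question.

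**2. What the documents give on early stopping.** They give no rate of stopping training before week 6 and no share of stoppers who are still tested. Three nearby figures are not stopping rates:

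- the C.5.3 statement that in earlier studies "patient compliance to training has ranged from 90 to 95" per cent;
- the 8% attrition by week 12 in C.1.3 (170 × 0.08 ≈ 14 patients);
- the 20% top-up trigger (34 of 170).

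**3. Illustration with assumed rates.** Let p be the share stopping before week 6, a the share of stoppers who are tested, and d the shortfall in stoppers' change. In the C.2.1 set, tested stoppers make up q = pa / (1 − p + pa) of an arm. The completer comparison differs from the C.2.1 comparison by d × (q₂ − q₁), in favour of the arm with more early stopping.

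Assume no true difference in the C.2.1 set, d of 0.5 to 1.0 SD (90 to 180 ft), and a simple baseline-to-12-week change score in place of the mixed model. For 5% against 15% stopping, the completer comparison has SE = 179.7 × √(1/80.75 + 1/72.25) = 29.1 ft.

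| Stopping by arm | Stoppers tested | q₂ − q₁ | Shift (ft) | Type I error |
|---|---|---|---|---|
| 5% v 15% | all | 0.1000 | 9.0–18.0 | 6.1–9.5% |
| 5% v 15% | half | 0.0554 | 5.0–10.0 | 5.3–6.4% |
| 5% v 15% | a quarter | 0.0293 | 2.6–5.3 | 5.1–5.4% |
| 5% v 15% | none | 0 | 0 | 5.0% |
| 5% v 10% | all | 0.0500 | 4.5–9.0 | 5.3–6.1% |
| 5% v 10% | half | 0.0270 | 2.4–4.9 | 5.1–5.3% |

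Equal stopping with equal shortfalls gives 0 ft. Swapping the arms reverses the sign.

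**4. Power under the two sets.** Assume 87.2 ft in music-arm patients who keep training, nothing in stoppers, equal stopping in both arms and all stoppers tested. With 8% attrition there are 85 × 0.92 = 78.2 per arm.

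| Stopping | All-randomised effect (ft) | Power, all randomised | Completers per arm | Power, completers |
|---|---|---|---|---|
| 5% | 87.2 × 0.95 = 82.8 | 82.2% | 78.2 × 0.95 = 74.3 | 84.1% |
| 10% | 87.2 × 0.90 = 78.5 | 78.0% | 78.2 × 0.90 = 70.4 | 82.1% |

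If stoppers keep half the gain, 10% stopping gives 82.8 ft and 82.2% power, against 82.1% for completers.

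**The case against.** The best defence is that C.2.1 is the section that specifies the primary analysis, and it already uses all the data. C.4.4.2 is a contingency note among miscellaneous limitations, and its wording includes patients without expressly excluding anyone. Read beside the stated purpose of the 6-week test, it may only mean that patients who leave after that test are kept. Its topic is withdrawal from the study, and a patient who withdraws before week 6 usually has no later walk test, so both readings then give nearly the same result.

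Most of this stands, and it limits the point. It does not remove the inconsistency: the sentence sets a training threshold that intent-to-treat does not need and C.2.1 does not contain.

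A reader might go further in four ways that the documents do not support.

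- **That the plan excludes early stoppers.** The sentence states a sufficient condition for inclusion and does not address the rest.
- **That the top-up rule shows such patients are replaced.** It fits equally well with protecting the number who have outcome data.
- **That the analysis set could be picked with knowledge of the arms**, because C.1.5 says the project manager, an exercise physiologist "and the statistician ([name]) will be aware of" group assignment. Nothing says the choice of set is left open for later, so this is speculation.
- **That type I error is 9.5%.** That value needs a threefold difference in stopping, a full 1 SD shortfall and every stopper tested, all of which are assumed.

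**Conclusion.** The defect stands in limited form and should be fixed. C.4.4.2 derives a post-randomisation criterion from intent-to-treat and is inconsistent with C.2.1. Harm arises only if the sentence is applied as an inclusion rule, and only through patients who stop training before week 6 and are still tested. Their number is unknown, so neither size nor direction can be stated. The shifts of 0 to 18 ft shown above illustrate a mechanism under assumed rates and are not a property of this plan. Nothing in the documents shows that early stopping will differ between arms. C.2.1 is written for COPD patients, so the conclusion concerns that cohort.

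**What to change.** Replace the sentence in C.4.4.2 with: *The primary analysis (C.2.1) includes all randomised patients in the arm assigned, using all available baseline, 6- and 12-week 6MWT data, whether or not they complete training.* Add that stopping training does not by itself end the scheduled tests for patients who remain in the study. The handling of patients who have to be withdrawn for medical reasons stays with the existing protocol.

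If a six-week-completer analysis is kept, label it as a sensitivity analysis. Leave the H3 set unchanged. The top-up rule may stay, with a note that added patients do not replace those already randomised.

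**Cost.** One replaced sentence and a short addition. The visits are already scheduled for every patient: at $20 a visit, two visits and an assumed 5–10% stopping, payments are 20 × 2 × 170 × 0.05 = $340 to 20 × 2 × 170 × 0.10 = $680, within the full-attendance schedule. The estimated effect and power may be slightly lower than in a completer analysis if stoppers gain less. At an assumed 10% stopping with 8% attrition, the loss is about 4 percentage points if stoppers gain nothing, and essentially none if they keep half the gain.
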